### 7.3 Criteria for Early Termination of Study Participation

Participants may voluntarily withdraw from the study for any reason at any time. The site investigator also may withdraw participants from the study to protect their safety and/or if they are unwilling or unable to comply with required study procedures. Participants also may be withdrawn if the study sponsor, government or regulatory authorities (including the Office of Human Research Protections), NICHD or site IRBs terminate the study prior to its planned end date. Every reasonable effort is made to complete a final evaluation of participants who withdraw or are withdrawn from the study prior to completing follow-up. Study staff members will record the reason(s) for all withdrawals in participants' study records.

### 7.4 Grading System

Due of the congruency of ATN's mission with that of HIV/AIDS Networks supported by the NIAID Division of AIDS (DAIDS), NICHD has adapted and implemented several DAIDS policies and requirements for the ATN. The Division of AIDS Table for Grading the Severity of Adult and Pediatric Adverse Events, Corrected Version 2.1 dated July 2017 and Addendum 3 (Rectal Grading Tables for Use in Microbicide Studies) will be the primary tools for grading adverse events for this protocol. Adverse events not included in those tables will be graded by the DAIDS AE Grading Table, Version 2.1 dated July 2017. In cases where an AE is covered in multiple tables, Addendum 3 (Rectal Grading Table for Use in Microbicide Studies) will be the grading scale utilized.

The DAIDS AE Grading Tables are available on the RSC website at https://rsc.niaid.nih.gov/clinical-research-sites/daids-adverse-event-grading-tables

#### **EAE Reporting Period**

- The expedited AE reporting period for this study is defined as the entire study duration for an individual participant (from enrollment until the participant's final study contact).
- After the protocol-defined AE reporting period, unless otherwise noted, only Serious Adverse Events (SAE) will be reported to NICHD if the study staff becomes aware of the events on a passive basis (from publicly available information).

#### 7.5 Adverse Events Definitions and Reporting Requirements

#### 7.5.1 Adverse Events

An adverse event is defined as any untoward medical occurrence in a clinical research participant administered an investigational product and which does not necessarily have a causal relationship with the investigational product. As such, an AE can be an unfavorable or unintended sign (including an abnormal laboratory finding, for example), symptom or disease temporally associated with the use of an investigational product, whether considered related to the product. This definition is applied to all the study groups, and is applied to all groups beginning from the time of enrollment. The term "investigational product" for this study refers to all study products listed in Section 5. Study participants will be instructed to contact the study site staff to report any AEs they may experience at any time between enrollment and completion of their participation. In the case of a life-threatening event, they will be instructed to seek immediate emergency care. Where feasible and medically appropriate, participants will be encouraged to seek evaluation where the study clinician is based, and to request that the clinician be contacted upon their arrival. Study site will obtain written permission from the participant to obtain and use records from non-study medical providers to complete any missing data element on a CRF related to an adverse event. All participants reporting an untoward medical occurrence will be followed clinically, until the occurrence resolves (returns to baseline) or stabilizes.

The study site investigators will determine AE resolution or stabilization in their best clinical judgment, but may seek medical consultation regarding follow-up or additional evaluations of an AE from the ATN MO and/or PSRT. Study site staff will document in source documents and case report forms all AEs reported by or observed in enrolled study participants regardless of severity and presumed relationship to study product. The Addendum 3 (Rectal Grading Tables for Use in Microbicide Studies) to DAIDS AE Grading Table Version 2.0 will be the primary tool for grading adverse events for this protocol. Adverse events not included in that table will be graded by the standard DAIDS AE Grading Table, Version 2.0 dated November 2014. In cases where an AE is covered in multiple tables, Addendum 3 (Rectal Grading Table for Use in Microbicide Studies) will be the grading scale utilized. Please see Data Safety and Management Plan for additional details.

#### 7.5.2 Serious Adverse Events

The OHRP guidance, "Guidance on Reviewing and Reporting Unanticipated Problems Involving Risks to Subjects or Others and Adverse Events," (OHRP, Appendix 10-09) defines a serious adverse event (SAE) as any adverse event that:

- Results in death,
- Is life-threatening,
- Requires impatient hospitalization or prolongation of existing hospitalization,
- Results in persistent or significant disability/incapacity,
- Results in a congenital anomaly/birth defect, or
- Is an important medical event that may not be immediately life-threatening or result in death or hospitalization but may jeopardize the patient or may require intervention to prevent one of the other outcomes listed in the definition above.

All serious adverse events will be reported to NICHD, as per the ATN Manual of Policies and Procedures, as well as the IRB of record. Please see Data Safety and Management Plan for additional details.

#### 7.5.3 Adverse Event Relationship to Study Product

The ATN Manual of Procedures and Policies (MOPP) notes in Section 10 that ATN investigators must determine how to assess AEs. Consistent with other HIV biomedical prevention trials, the relationship of all AEs to study product will be assessed per the *Manual for Expedited Reporting of Adverse Events to DAIDS* (Version 2.0, dated January 2010), the Investigator's Brochures, and clinical judgment. Per the Manual for Expedited Reporting of Adverse Events to DAIDS (Version 2.0, dated January 2010), the Investigator's Brochures, and clinical judgment. Per the Manual for Expedited Reporting of Adverse Events to DAIDS (Version 2.0, dated January 2010), the relationship categories that will be used for this study are:

- *Related*: There is a reasonable possibility that the AE may be related to the study agent(s)
- *Not related*: There is not a reasonable possibility that the AE is related to the study agent(s)

When an AE is assessed as "not related" to study participation, an alternative etiology, diagnosis, or explanation for the AE should be provided. If new information becomes available, the relationship assessment of any AE will be reviewed again and updated, as required.

### 7.6 Expedited Adverse Event (EAE) Definitions and Reporting Requirements

### 7.6.1 Expedited Adverse Event Reporting

Per ATN policies, SAEs of any severity grade, AEs of severity grade 3 or higher that are determined to be related to study participation or intervention, and UEs that are severity grade 3 or higher will be reported immediately.

### 7.6.2 EAE reporting procedures specific to this protocol

Events that meet SAE criteria and are unexpected (not previously reported to the agency or included in the IB) must be reported in an expedited manner. The IND Sponsor will assume responsibility for the reporting of Serious Adverse Events to the FDA and regulatory agencies outside the U.S., as appropriate per 21 CFR 312.32 and 21 CFR 312.33. Copies of this final report will be filed with the DREAM Regulatory Core.

If the event is assessed as reportable to the FDA in an expedited manner, the DREAM Regulatory Core will draft the report in narrative format and will distribute to the ATN MO and the IND Sponsor for review and approval. Once the review is complete, the DREAM Regulatory Core will generate a final version of the expedited safety report and will provide it to the IND Sponsor with a cc to the ATN MO via secure e-mail submission at the following address:

[name]. E-cubed Consulting, LLC [name]

In case of a fatal or life-threatening suspected adverse reaction, the IND Sponsor will notify the responsible review division of the FDA by telephone or facsimile transmission as soon as possible but in no event later than 7 calendar days after the receipt of the respective adverse event information and determination that it meets the respective criteria for reporting. Any additional information received must be sent to the agency as soon as possible, but no more than 15 days after receipt of the information.

## 7.6.3 Expedited Adverse Event (EAE) Reporting Requirements for this Study

The study agent, for which expedited reporting is required, is:

• Rectal TFV douche – 5.28 mg/mL (\*660 mg in 125 mL) in hypo-osmolar solution

## 7.7 Dose Modification

This is a single dose administration protocol. Adverse event assessments will be made in collaboration with the Protocol Safety Review Team (PSRT), who will review all study AEs, with special attention to the events

and toxicities assessed to be greater than Grade 2. The determination as to whether dose administration in additional participants is justifiable and compatible with the mandate for participant safety will be based on this assessment. Please see detailed Data Safety and Management Plan for additional information.

#### 7.8 Discontinuation of Study Product(s) in the Presence of Toxicity

Each participant will receive one dose of the study product, administered in clinic. If study site investigator has an acute concern about the safety of any product administration, may withdraw the participant from the study. Please see Data Safety and Management Plan for additional details.

#### 7.9 Reporting of Adverse Reactions to the Responsible IRBs

The study site investigator will report adverse reactions to the responsible IRBs in accordance with respective IRB policies and procedures.

Follow-up information to a reported adverse event will be submitted to the IRB as soon as the relevant information is available. If the results of the study site investigator's follow-up investigation show that an adverse event that was initially determined to not require reporting to the IRB does, in fact, meet the requirements for reporting, the study site investigator will report it as soon as possible in accordance with respective IRB policies and procedures. Please see Data Safety and Management Plan for additional details.

#### 7.11 Withdrawal of Subjects Due to Adverse Events

If a participant has a Grade 2 or higher AE associated with the study, he has met a study end point and will be referred to local care and treatment services. He may return to the research clinic for additional counseling and other support services, as needed. Continued study participation would be of no added benefit; thus follow-up visits will be discontinued and the participant will be considered terminated from the study. An Early Termination Visit will be conducted, if the participant is willing. Please see Data Safety and Management Plan for additional details.

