#### Safety

Adverse Events Grade 2 or higher clinical and laboratory adverse events as defined by the Division of AIDS Table for Grading the Severity of Adult and Pediatric Adverse Events, Version 2.1 dated Jul 2017 and Addendum 3, Rectal Grading Table for Use in Microbicide Studies.

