# Table 10: Visit 3 – Dosing Visit (Day 1)

 Safety labs will be drawn prior to dosing and initiation of any specimen collections.

\* Post-dose PK collection time points are approximate. Every effort will be made to adhere to the timeline, however, due to logistics, timing will not be exact and specimen collections may be missed (i.e. during biopsy collection). \*\*Biopsies taken depend on participant's individual sampling schedule

\*\* Biopsies and post-dose rectal fluid collection taken depend on participant's individual sampling schedule

\*\*\* Microbiome and rectal fluid collection should be done prior to dosing or enema administration and microbiome collection should precede rectal fluid collection.

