## 6.7 Visit 6- Termination Visit- 96 hour (Day 5 + 3 days)

The Termination Visit ideally should occur at 96 hours (+3 day window) for all participants. The term visit should be at least 24 hours after the last scheduled biopsy. This visit will serve as the participant's study termination.

During their Termination Visit, participants will complete an exit in-depth interview (IDI) that will explore their experiences participating in the study, user-centered suggestions for product design and delivery, factors influencing product use in the future, and suggestions to maximize YMSM's engagement in future biomedical trials, including how to overcome perceived barriers and challenges based on their experiences. The IDI will be conducted using video-conferencing by a trained interviewer located at the University of Pennsylvania.

If a participant withdraws from study participation early or is withdrawn early from study participation by the study team, they will be asked to come in for an Early Termination Visit and the all the activities conducted at the Termination Visit will also be conducted for the Early Termination Visit.

Component	Procedure/Analysis	
Administrative	
 
Review/update demographic and locator information
 
Review STI risk reduction counseling and provide condoms
 
	
Clinical	
 
Review/update medical history
 
Review/update concomitant medications
 
Review any available test results
 
Complete AE assessment
 
Symptom-directed physical exam as needed
 
Obtain vital signs (HR, BP, Temp)
 
Collect blood specimens for:
 
	
Safety Labs and STI Screening: blood	
 
Collect blood specimens for:         
 
CBC with differential
 
CMP
 
HIV-1 antigen/antibody 4th generation testing (confirmatory tests as needed) *
 
Syphilis Testing (confirmatory test as needed) *
 

 
 
 
	
Safety Labs and STI Screening: urine and rectal	
 
Collect urine sample for GC/CT (NAAT) *
 
Collect rectal swab for GC/CT (NAAT) *
 
Collect swab for HSV, if indicated *
 
	
Other Specimens (rectal fluid, etc.)	• Collect specimens as appropriate/indicated (if the participant is willing) *	
Behavioral	Completion of exit in-depth interview	

Activities to take place at the Termination Visit include: **Table 12: Termination Visit** 

\*If indicated and/or per local standard of care.

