#### Table 13: Interim Visit

#### 6.10 Participants Who Withdraw or Are Withdrawn from the Study

If the participant withdraws or is withdrawn from the study after receiving study product, an Early Termination Visit will be conducted, if possible. The protocol principal investigator in consultation with the site investigator will determine if research participants who fail to complete all biopsy collection sessions should be replaced. Replacement subjects would be assigned the same sampling schedule as the subject they are replacing.

Any participant with quantifiable plasma TFV/FTC or PBMC TFV-DP/FTC-TP concentrations at the Enrollment Visit (Visit 2) will be replaced.

Participants with quantifiable plasma tenofovir/emtricitabine concentrations at Visit 2 will not proceed to the tenofovir douche administration and pharmacokinetic sampling portion of the protocol. These participants may continue to participate in the In-Depth Interview portion of the protocol.

PBMC TFV-DP/FTC-TP concentrations will be measured periodically. Participants with quantifiable TFV/DP/FTC-TP concentrations may continue to the TFV douche administration and pharmacokinetic sampling portion of the protocol, but may be replaced once the PBMC TFV-DP/FTC-TP results are available.

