Safety: To evaluate the safety of a single dose of a TFV douche when applied rectally, as measured by the number of  $\geq$ Grade 2 adverse events (AEs) as defined by the Division of AIDS Table for Grading the Severity of Adult and Pediatric Adverse Events. For the safety analysis, the number and the frequency of all adverse events (AEs) will be tabulated. A single summary outcome of this type (yes/no) can be reasonably assumed to follow a Bernoulli distribution. Assuming a true underlying rate of one or more participants experiencing AEs is between 0.01 and 0.20 in a sample of 16 YMSM, there would be a 81% chance that one or more participants might experience an AE when the true rate is at least 10% and a probability less than 15% when the true rate is no more than 1%. Unless the true rate is at least 3%, the probability of two or more subjects experiencing AEs will be quite small – less than 5%. Additional safety analyses will also tabulate the number and type of AEs observed overall, and by severity, site, and study product. AEs that lead to discontinuation of study participation will be tabulated separately.

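### Section 7.11 ends scheduled follow-up at the first study-associated Grade 2+ adverse event, so later separate events, or a laboratory change by 96 h, can go unrecorded in the few participants affected

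*Combined protocol and SAP*

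**What the plan says.** The primary safety endpoint in Section 2.2 is "Grade 2 or higher clinical and laboratory adverse events". Section 9.6 measures safety by the number of such events. It tabulates the number and frequency of all adverse events, including by severity, and adds that "AEs that lead to discontinuation of study participation will be tabulated separately".

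Section 7.11 says that a participant with a study-associated Grade 2+ event has met an end point and gains nothing by continuing, "thus follow-up visits will be discontinued and the participant will be considered terminated from the study". An Early Termination Visit follows if he is willing.

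Other sections soften this:

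- Section 6.7: the "activities conducted at the Termination Visit will also be conducted for the Early Termination Visit", which includes an adverse event assessment, CBC and CMP.
- Section 6.10: after withdrawal following study product, "an Early Termination Visit will be conducted, if possible".
- Section 7.3: "Every reasonable effort is made to complete a final evaluation of participants who withdraw or are withdrawn from the study".
- Section 7.5.1: "All participants reporting an untoward medical occurrence will be followed clinically, until the occurrence resolves (returns to baseline) or stabilizes".

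Section 7.8 confirms that each participant receives one dose, in clinic.

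**The concern.** The reason given in 7.11 holds only if nothing after the first qualifying event matters to the endpoint. Under 9.6 it does matter: a second Grade 2+ event adds to the count, and a worse one changes the severity table. The rule removes scheduled detection in exactly the participants who have already shown a study-associated reaction.

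With a single dose, stopping visits after dosing cannot prevent further exposure. It can prevent only the remaining procedures: sigmoidoscopy with biopsy, anoscopy and the 72 h cleansing enema.

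At stake is a somewhat understated safety profile in a 16-person trial that enrols from age 15. Under Section 7.7, the safety review team also uses the adverse events seen so far to decide whether dosing further participants is justified.

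**Working it through.** **1. The plan's own figures.** Section 9.6 gives an 81% chance of at least one affected participant at a true rate of 10%, and under 15% at 1%. With n = 16:

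- 1 − 0.90^16 = 0.815
- 1 − 0.99^16 = 0.149

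Both reproduce. They concern whether a participant has any event. A participant who triggers 7.11 already counts as yes, so the rule does not disturb them.

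**2. What is scheduled after dosing (Appendix I).** Adverse event assessments fall at Visits 4 (24 h), 5 (72 h) and 6 (96 h). Plasma/PBMC draws fall at 1, 6, 24 and 72 h. CBC/CMP are drawn at Visits 1, 3 and 6. The Visit 3 panel is pre-dose (Table 10, footnote 1: "Safety labs will be drawn prior to dosing and initiation of any specimen collections"), so Visit 6 holds the only scheduled post-dose panel.

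**3. What 7.11 removes, by timing of the event.**

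| Event recognised | AE assessments still scheduled | Under 7.11 | Plasma/PBMC draws lost | Post-dose CBC/CMP |
|---|---|---|---|---|
| Dosing day, after 6 h draw | 3 (Visits 4, 5, 6) | at most 1 | 2 of 4 (24 h, 72 h) | possibly earlier than 96 h, or missed |
| Visit 4, after 24 h draw | 2 (Visits 5, 6) | at most 1 | 1 of 4 (72 h) | same |
| Visit 5, after 72 h draw | 1 (Visit 6) | at most 1 | 0 | same |
| Visit 6 | 0 | no change | 0 | no change |

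The first row is the worst case. The protocol does not fix when the Early Termination Visit takes place.

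**4. Can one participant have several Grade 2+ events?** In the Product C phase of DREAM-01 (Table 4), participants with events number 3 at Grade 2 and 1 at Grade 3, so at most 3 + 1 = 4 people. The events number 7 + 1 = 8. Several Grade 2+ events in one person therefore did occur. These are all-cause events with no timing given, so they are not a rate for 7.11.

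**5. How many participants might be affected?** Section 1.6 reports two product-related events among 18 DREAM-01 participants, both Grade 1. That is 0 of 18 with a product-related Grade 2+ event.

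- Exact two-sided 95% upper limit per participant: 1 − 0.025^(1/18) = 0.185. Applied to 16 people: 16 × 0.185 = 3.0.
- Each DREAM-01 participant was to receive three formulations, so that limit covers three doses. Assuming all 18 × 3 = 54 doses were given, with equal and independent risk per dose: 1 − 0.025^(1/54) = 0.066. Applied to 16 single doses: 16 × 0.066 = 1.1.

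The observed number is zero in both cases. No rate is given for procedure-related events, which 7.11 may also cover, since it does not define association with the study.

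**The case against.** The strongest reply has four parts.

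- **The summary outcome is safe.** Section 9.6 frames safety for 16 participants as a yes/no outcome, and anyone who triggers 7.11 is already a yes. This stands. A reader might infer that the primary incidence is biased; it is not. What can suffer is the event count and the maximum grade.
- **The PK loss is refilled.** Section 9.7 requires PK data for all periods or replacement of the participant, and replacements take the same sampling schedule. Sections 6.10 and 9.7 also contain discretionary wording, but the PK effect is minor. Replacement does not recover the safety follow-up of the person who had the event.
- **There are safeguards.** The Early Termination Visit has full Visit 6 content. Section 6.8 allows a final contact, and Section 6.9 allows interim visits prompted by adverse events. A reader might infer that a participant with a Grade 2+ event is abandoned; Section 7.5.1 rules that out for the reported event. None of these keeps the Day 2 and Day 4 assessments or plans surveillance for new events, and 6.9 applies during the study, so its use after termination is unclear. The Data Safety and Management Plan cited in 7.11 is not among the documents and may add follow-up.
- **Stopping is kind to the participant.** Sparing a healthy young volunteer further biopsy, anoscopy or enema after a moderate event is defensible. It does not justify dropping an adverse event assessment or a blood draw he is willing to have.

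A reader might also infer from Section 13.3 that data collection is barred after termination. The triggers listed there are withdrawn consent, cancellation of the study and death, so the bar probably does not reach these participants.

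**Conclusion.** The point holds, at minor severity. The stopping rule in 7.11 does not match an endpoint that counts events and grades. In an affected participant, up to three scheduled assessments shrink to at most one voluntary visit, and the only scheduled post-dose laboratory panel may come early or not at all. New separate events or a higher maximum grade can therefore be missed. Because "AEs that lead to discontinuation of study participation will be tabulated separately", the affected participants will be visible in the tables, but what went unobserved in them will not.

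Few participants are likely to be affected, possibly none. The product-related upper limit is about 1 of 16 if risk is equal and independent per dose, or about 3 of 16 if the three-dose limit is applied unchanged. A reader might apply the 1% to 20% planning range in 9.6 and infer a 15% to 97% chance that the rule is triggered. The documents do not support that, because the range is not restricted to study-associated Grade 2+ events. The conclusion also assumes that the unseen safety plan does not already keep these visits.

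**What to change.** Amend 7.11 so that, after a post-dose Grade 2+ adverse event, the remaining biopsy, anoscopy and cleansing enema may be stopped at the investigator's discretion. The already scheduled adverse event assessments, plasma/PBMC draws and 96 h CBC/CMP continue for participants who are willing. Limiting the change to post-dose events leaves intact the option of not dosing someone who has such an event before Visit 3.

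Two clarifications would help in the same edit: whether study-associated includes procedure-related events, and that the bar in 13.3 does not apply here. Section 9.7 already provides for using all available safety data, so the analysis text needs no change.

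The cost is a few sentences, plus a few already scheduled visits kept for participants who have had an event. No new visits, samples or procedures are added.
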